1.3.4. Reader-02 Study

The Reader-02 Pivotal Study met its primary endpoint and demonstrated that Imagio Breast Imaging Gen 1 System has better specificity than IUS at a fixed sensitivity of 98%. Specificity at a fixed sensitivity of 98% was analyzed using multi-reader multi-case (MRMC) analysis (Obuchowski-Rockette Dorfman-Berbaum-Metz (ORDBM) MRMC 2.51). Mean (average over all readers) fixed specificity (fSp) was found to be higher with statistical significance (two-sided $p=0.027$) for IUS+OA (47.2%, 95% CI=[35.9%,58.5%]) compared to IUS alone (38.2%, 95% CI=[24.9%, 51.6%]), with a difference in fSp of 9.0% (95%CI=[1.0%, 17.0%]). Thus, IUS+OA achieved the primary endpoint in the Reader-02 Pivotal Study. The decrease (i.e., improvement with IUS+OA compared to IUS alone) in negative likelihood ratio (NLR) could not be established with statistical significance because the observed relative NLR (the ratio in NLR for IUS+OA and IUS) was 0.896 with a 95% CI=(0.693, 1.11) which included 1, indicating that no evidence of a difference in NLR was found. Based on descriptive statistics that do not control type I error and that cannot be generalized outside this particular study, the observed mean positive likelihood ratio (PLR) was 1.959 (95% CI: 1.870, 2.051) for IUS+OA (only as a descriptive result this suggests that averaging over all 15 readers in the study a positive test read (POM>2%) was observed about 2 times more often among cases with cancer, compared to those without cancer), and the mean PLR was reported as 1.548 (95% CI: 1.498, 1.597) for IUS alone (only as a descriptive result this suggests that averaging over all 15 readers in the study a positive test read (POM>2%) was observed about 1.5 times more often among cases with cancer, compared to those without cancer). The descriptive observed relative PLR was 1.281 (95% CI: 1.231, 1.298).

Partial area under the curve (pAUC) was lower in the hierarchical test order than NLR, which failed to achieve significance. Consequently, pAUC results are not part of the claim structure and are reported as descriptive statistics. The mean unscaled pAUC was 0.0244 (95% CI: 0.0230, 0.0258) for IUS+OA and 0.0205 (95% CI: 0.0191, 0.219) for IUS alone, with a difference of 0.0039. All readers had a larger point estimate of pAUC for IUS+OA than for IUS alone.

Of the 480 subjects who contributed masses for reading in the Reader-02 study, 16 (3.3%) experienced at least one AE during the study, of which 6 (1.3%) occurred on the date of the Imagio procedure. Three subjects (0.6%) had at least one Imagio procedure-related AE. There were no AEs that were graded as severe; 14 (2.9%) were considered mild and two (0.4%) were graded moderate. All Imagio procedure-related AEs were considered mild. Two subjects (0.4%) experienced a serious adverse event (SAE), neither of which was Imagio procedure-related; one experienced rupture of a saline breast implant, requiring revision surgery, and one was diagnosed with Stage I non-small cell lung cancer and underwent resection of the affected lobe in the right lung. There were no SADEs or UADEs.

1.3.5. MAESTRO Post-Marketing Study – Europe

Another prospective multi-center study included results of 209 subjects with the Imagio Gen 1 enrolling 215 breast masses classified as BI-RADS 4a or 4b by CDU [11]. Subjects were enrolled at 5 sites between 2015 and 2016. Masses that were classified as BI-RADS 4a or 4b by CDU were

entered into the MAESTRO study, and all were biopsied. The absolute OA/US specificity was 41.1% and the improvement in specificity with OA/US was also 41.1% because, by definition, the CDU findings in any benign mass classified as BI-RADS 4a or 4b would be falsely positive and specificity for CDU will be 0%. The OA/US sensitivity in MAESTRO was 95.5%. The NLR was 0.11. There was one moderate adverse event, a hematoma post biopsy, that was unlikely related to the OA/US procedure.

1.4. Study Motivation and Rationale

This study performs the first clinical evaluation of the Gen 2 Imagio System in a clinical setting to assess image quality with both the IUS ultrasound only probe and the OA/US (duplex probe). This study assesses palpable and non-palpable breast abnormalities in adult subjects who are referred for a diagnostic imaging breast work-up, following clinical presentation, or screening mammography, or diagnostic mammography, or other imaging examinations.

2. STUDY DESIGN AND OBJECTIVES

This clinical investigation is designed to evaluate the images produced by the Gen 2 Imagio System in a clinical setting.

The primary objectives of this study are:

1. Obtain ultrasound only probe images and OA/US (both gray scale and OA) probe images. This includes doppler and elastography imaging with gray scale only ultrasound probe and ultrasound mode of the duplex OA/US probe.
2. Provide breast and lymph node pathology results (except BI-RADS 1, 2 and 3 (as applicable))

3. SUBJECT POPULATION

A maximum of 38 healthy subjects ≥ 18 years old will be enrolled in the study. The 38 subjects will include the following via Mammo (BI-RADS 1 and 2) or CDU:

- 4 Subjects with BI-RADS 1
- 4 subjects with BI-RADS 2
- 8 subjects with BI-RADS 3
- 8 subjects with BI-RADS 4a
- 4 subjects with BI-RADS 4b
- 4 subjects with BI-RADS 4c
- 6 subjects with BI-RADS 5

3.1. Inclusion/Exclusion Criteria

Inclusion Criteria: Subjects must meet all the following criteria to be included in the study:

1. Has a signed and dated informed consent, prior to initiation of any study-related activities.
2. Is at least 18 years of age.
3. Have been referred for a breast US because of a breast lesion/mass finding via a palpable lump or per standard of care imaging.
4. Is willing and able to comply with protocol-required scans.

Exclusion Criteria: Subjects who meet any of the following criteria will be excluded:

1. Is pregnant or lactating.
2. Has a condition or breast impediment (i.e. insect bites, poison ivy, rash, open wounds, chafing of the skin, scar, tattoos, moles, hematoma, nipple rings, etc.) which could interfere with the intended field of view.
3. Is experiencing photo-toxicity associated with currently taking, or having taken, photosensitizing agents within the previous 72 hours such as some sulfur containing drugs, ampicillin, tetracycline.
4. Is currently undergoing phototherapy.
5. Has a history of any photosensitive disease (e.g., porphyria, lupus erythematosus) or undergoing treatment for a photosensitive disease and is experiencing photosensitivity.
6. Has had an adverse reaction in the past to medical laser procedures, such as laser hair removal or laser tattoo removal.
7. Has had prior benign excisional breast biopsy on breast of interest within the past 18 months.
8. Currently has mastitis.
9. Prisoners

These inclusion and exclusion criteria will be confirmed prior to the start of each scan procedure.

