3.3. Enrollment Failures

Subjects deemed enrollment failures according to the quality assurance review or failure to complete the biopsy evaluations for BI-RADS 3 (as applicable), BI-RADS 4 and 5 will be replaced during the active enrollment period of the study. The following subjects will be considered enrollment failures and will be followed until all AEs are resolved:

- Subjects found to be ineligible after the scan is conducted
- Subjects for whom the study device scans do not pass review (Imaging Core Lab Quality Assurance Radiologist (QAR) review)
- BI-RADS 3 (as applicable) 4 and 5 subjects who have incomplete or unusable biopsy results

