7.1.2. Demographics, Medical History, and Other Baseline Characteristics

For the full analysis set (FAS) population (defined in section 6.3), baseline subject characteristics will be tabulated. Baseline subject characteristics will comprise the following: subject demographics (gender, age, race, ethnicity), height, weight, Fitzpatrick skin type, menopausal status, cup size, Standard of Care (SOC) imaging (i.e. mammography, CDU, and magnetic resonance imaging) POM and BI-RADS, breast mass location and depth and size, lymph node location and size and depth, breast and lymph node medical/surgical history.

For baseline subject characteristics that are continuous variables, the following descriptive statistics will be given: number of observations, mean, standard deviation, minimum, maximum, and median. For subject characteristics that are categorical variables, the frequency and percentage of subjects in each category will be provided. Summary tables will display demographic and baseline characteristics overall and by BI-RADS of the breast masses (3, 4a, 4b, 4c, 5).

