7.2. Sample size

A maximum of 38 healthy subjects ≥ 18 years old will be enrolled in the study. The 38 subjects will include the following:

- 4 subjects with BI-RADS 1- can be recruited from BI-RADS 0. (Ex. Mammographic asymmetry caused by normal breast tissue, breast pain, etc.)
- 4 subjects with BI-RADS 2- can be recruited from BI-RADS 0. (Ex. palpable lipoma, simple cyst, ductasia, angioma, etc.)
- 8 subjects with BI-RADS 3
- 8 subjects with BI-RADS 4a
- 4 subjects with BI-RADS 4b
- 4 subjects with BI-RADS 4c
- 6 subjects with BI-RADS 5

Given the nature of the study no formal hypothesis testing is planned, and formal power and sample size calculations were not performed. A sample size of 38 subjects is deemed adequate to provide a cross section of breast masses/lesions and lymph nodes.

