7.3. Analysis populations

7.3.1. Full Analysis Set (FAS) Population

The FAS population will be defined as all consented subjects who completed screening/enrollment and had a successful Imagio imaging procedure. The FAS population will be used as the secondary analysis population for the study endpoints.

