7.3.2. Per-protocol (PP) Population

The PP population will be defined as all FAS subjects described above who meet the study eligibility criteria and have no other major protocol violations. The PP population will be used for primary analysis of the study endpoints.

Within the PP population, summaries of each study endpoint will be provided overall and by

subgroups based on BI-RADS (3, 4a, 4b, 4c, 5) of the breast masses.

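### Do the breast-pain example in Section 7.2 and the missing BI-RADS 1 and 2 table rows require a change to the plan?

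*Combined protocol and SAP*

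**What the plan says.** **Eligibility.** Section 3.1 makes every inclusion criterion mandatory. Criterion 3, repeated in the synopsis, is "Have been referred for a breast US because of a breast lesion/mass finding via a palpable lump or per standard of care imaging". The same section adds: "These inclusion and exclusion criteria will be confirmed prior to the start of each scan procedure". Section 7.2 allows the four BI-RADS 1 places to be filled from subjects assessed as BI-RADS 0 and gives examples: "Mammographic asymmetry caused by normal breast tissue, breast pain, etc". Section 3 says the BI-RADS 1 and 2 places are identified by mammography or conventional ultrasound.

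**Consequences of ineligibility.** Section 3.3 counts among enrollment failures "Subjects found to be ineligible after the scan is conducted". Section 7.3.2 defines the primary analysis set by eligibility: "The PP population will be defined as all FAS subjects described above who meet the study eligibility criteria".

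**Table strata.** Section 7.3.2 asks for endpoint summaries overall and by "subgroups based on BI-RADS (3, 4a, 4b, 4c, 5) of the breast masses". Section 7.1.2 uses the same list for the baseline tables, which are run on the FAS. Section 7.3.1 defines the FAS as "all consented subjects who completed screening/enrollment and had a successful Imagio imaging procedure", with no restriction by BI-RADS. Section 7.1.1 asks more generally for summaries overall and by BI-RADS, and gives no list of categories.

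**The concern.** Two things look wrong on a first reading.

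First, pain is neither a palpable lump nor an imaging finding. A recruiter who follows the example in Section 7.2 could enrol a subject whom criterion 3 does not admit. If this were found only after the scan, she would become an enrollment failure and drop out of the primary per-protocol set.

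Second, the plan enrols seven BI-RADS categories but lists five for tabulation. The overall column of the baseline tables could then exceed the sum of its rows, with no row describing the extra subjects. At stake are the clarity of eligibility and of the table denominators.

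**Working it through.** **Inputs.** The quotas by BI-RADS category (synopsis, Sections 3 and 7.2) are 1: 4; 2: 4; 3: 8; 4a: 8; 4b: 4; 4c: 4; 5: 6. The stated maximum is 38.

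**Reproducing the plan's figure.** 4 + 4 + 8 + 8 + 4 + 4 + 6 = 38, which agrees.

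**Size of the table gap.**
- Places in the listed strata: 8 + 8 + 4 + 4 + 6 = 30, and 30/38 = 78.9%.
- Places with no listed row: 38 − 30 = 8, and 8/38 = 21.1%. These are two of the seven categories.

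**What a reader can recover.** Suppose each subject sits in one row and all planned places are filled and imaged. For any categorical baseline variable, the BI-RADS 1–2 count is the overall count minus the sum of the listed rows. For a continuous variable with complete data, the BI-RADS 1–2 mean is

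(38·m_all − 8·m_3 − 8·m_4a − 4·m_4b − 4·m_4c − 6·m_5) / 8.

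If each printed mean is rounded with error at most e, the recovered mean is off by at most (38 + 30)·e/8 = 8.5e. Medians, minima and maxima cannot be recovered this way. Standard-of-care BI-RADS is itself one of the baseline variables tabulated under Section 7.1.2, so the number of BI-RADS 1 and 2 subjects should be visible directly.

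**Where the gap can appear.**
- Baseline tables on the FAS: yes.
- Ultrasound feature scores: only where they are recorded for BI-RADS 1 or 2.
- Pathology: little or none, because objective 2 in Section 2 excepts BI-RADS 1 and 2.
- Opto-acoustic scores: little or none. Section 1.2 says this mode is not indicated for BI-RADS 1 and 2, and footnote 2 of Table 1 makes the duplex probe only a possibility for them.
- SenoGram summaries: little or none, because Section 1.1.2 requires five opto-acoustic scores as input.
- Safety tables: Section 7.1.4 carries no restricted list.

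**Size of the eligibility question.** The floor is 0 subjects. The ceiling is all four BI-RADS 1 places filled by subjects with pain and no lump or imaging finding: 4/38 = 10.5%. At that ceiling, if all four were excluded, the planned per-protocol total would fall from 38 to 34. The five listed strata would stay at 30.

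**Do the two passages collide?** Section 7.2 does not say pain alone. Pain appears as one item in an open list of examples, under a sentence about subjects who already have an imaging assessment. Criterion 3 has a route through standard-of-care imaging. That does not prove that every such subject has a lesion or mass finding, but a subject with pain and a finding meets both passages. A subject with pain and no finding is stopped by Section 3.1 at the check before the scan. The quota can be filled with no conflict.

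**The case for a change.** The case for acting is that an open list should still not name a source that a mandatory criterion may refuse. Consent counts as enrollment (Section 3.2) and enrollment is capped at 38, so a mistaken recruit could use up a place. The replacement sentence in Section 3.3 mentions quality review and incomplete biopsy, not ineligibility. On the tables, the strata are described as those of breast masses, which may explain leaving out BI-RADS 1. It explains BI-RADS 2 less well, since the examples in Section 7.2 include lipoma and simple cyst. Nor does the plan say which BI-RADS assessment (mammography, conventional ultrasound or Imagio) defines the rows. The repair would be a few words and one row.

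Much of this stands as a comment on drafting. The lists are incomplete for BI-RADS 2, and the row variable is left to the analyst. But the check before each scan already guards against the mistaken recruit, and the places at risk are at most four in a category with no planned pathology result. Nothing in the plan calls the lists exhaustive, and Section 7.1.1 leaves room for a further row. Adding rows is also not a clear gain for the endpoint summaries. If a BI-RADS 1–2 row were added there while the overall column was kept to BI-RADS 3–5 masses, the rows would exceed the total, which is the same mismatch in reverse.

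**Conclusion.** No change to the plan follows. The breast-pain example is a loose illustration in a sample-size section, and the governing criterion overrides it before any scan. It affects 0 to 4 of a maximum of 38 subjects, and 0 is plausible because the quota can be met from other sources. The row lists leave out 8 of 38 planned places (21.1%), chiefly in the FAS baseline tables. A competent analyst would show the denominators or add a row under Section 7.1.1.

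These sizes assume full enrollment to quota, one row per subject and successful imaging in all. The actual FAS may be smaller, since 38 is a maximum. The study has no hypothesis test and no power calculation (Section 7.2), so no inference or sample size depends on either point. Tidier wording would help a reader but would not alter what the trial does or what it can conclude.

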Intervention	Each subject will have the breast and, as applicable, the axillary lymph nodes imaged with the Gen 2 Imagio system.
Duration of study visit	One visit of up to 60 minutes unless Imagio imaging needs to be done again
Total duration	6 months
Clinical investigation population	
Sample size	
A maximum of 38 healthy subjects ≥ 18 years old will be enrolled in the study. The 38 subjects will include the following:
 
 - 4 BI-RADS 1 - 4 BI-RADS 2 - 8 subjects with BI-RADS 3 - 8 subjects with BI-RADS 4a - 4 subjects with BI-RADS 4b - 4 subjects with BI-RADS 4c - 6 subjects with BI-RADS 5
Inclusion criteria	
Subjects must meet the following criteria:
 
 - Signed and dated informed consent, prior to participating - At least 18 years of age - Have been referred for a breast US because of a breast lesion/mass finding via a palpable lump or per standard of care imaging - Willing and able to comply with protocol required scans
Exclusion criteria	
Subjects who meet any of the following criteria will be excluded:
 
 - Pregnant or lactating - Has a condition or breast impediment at a location where the duplex probe will be in contact with the subject, which could interfere with the intended field of view - Photo-toxicity associated with currently taking, or having taken, photosensitizing agents within the previous 72 hours - Currently undergoing phototherapy - History of photosensitive disease or undergoing treatment for a photosensitive disease and is experiencing photosensitivity

	
 - Previous adverse reaction to medical laser procedures - Prior benign excisional breast biopsy on breast of interest within the past 18 months - Current mastitis -Prisoners
Statistical analysis	

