1.3.1. Feasibility Study

A feasibility study was conducted using a total of 155 subjects to determine the ability of Imagio Gen 1 to detect benign and malignant features. The feasibility study provided data to further develop an algorithm to identify separate sets of features that characterize benign and malignant disease. The study included subjects with negative diagnostic ultrasound results and positive diagnostic ultrasound, including results of varying histopathology diagnoses, sizes, locations, depths, ages, ethnicities, and races. These subject-specific characteristics were intended to identify any unusual subpopulations. Exclusions for this study on the use of OA included pregnant subjects, males, subjects with obscured views, and subjects on medications that could activate dermatologic conditions (e.g. photosensitive skin conditions).

The feasibility study demonstrated internal and external features representing tumor morphology [4-6]. The reader assigned POM was significantly higher for malignant masses than for benign masses [7]. The specificity was 8% higher for Imagio than for conventional diagnostic ultrasound (CDU) (24% for OA vs 16% for CDU) among those with benign disease, there was >40% relative reduction in the numbers with POM >2% in support of biopsy sparing [8]. Among subjects with benign disease, 54% of BI-RADS 4a subjects and 23% of BI-RADS 4b subjects had an Imagio POM <2% in support of downgrading [9]. There were no adverse events reported.

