3.2. Informed Consent

Written informed consent will be obtained from every subject. Once consented, the subject will be considered enrolled in the study. Screen failure data will be collected. A subject is considered a screen failure post signing the informed consent.

The informed consent interview will be performed, and each subject will be given personal time and the opportunity to ask questions. The time for decision making prior to giving consent or declining participation will include the time to slowly read and to discuss the consent form. The IUS (ultrasound only probe) and OA/US (duplex probe) imaging procedure will be performed after consent. The subject will receive a copy of the Informed Consent Form for their records.

Upon enrollment, subjects receive a subject number that will be used on all documentation for the subject throughout the study. Subject numbers will be assigned in ascending order, and numbers will not be omitted or reused. The subject number is coupled with the site identification number for

unique identification of each subject.

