4.3. Subject Data

Data to be collected:

- Gender
- Age
- Race
- Ethnicity
- Fitzpatrick skin type
- Breast and lymph node medical/surgical history

- Height
- Weight
- Inclusion/Exclusion criteria review
- Breast Mass location and depth and size
- Breast Mass feature Scores
- Image Artifact Score
- Lymph node location and size and depth
- Lymph Node Scoring
- Standard of Care (SOC) Imaging POM and BI-RADS
- Imago IUS POM and BI-RADS using ultrasound only probe and OA/US POM and BI-RADS post SenoGram for breast mass
- IUS ultrasound only probe imaging, duplex OA/US probe imaging (doppler and elastography images as applicable with duplex OA/US probe in ultrasound only mode), and SOC imaging for each breast study mass and study lymph node (as applicable)
- Breast biopsy images for ultrasound only probe and duplex OA/US probe in ultrasound only mode and pre and post biopsy duplex OA/US probe in OA mode images as possible
- Mass and lymph node pathology and surgical report for BI-RADS 3 (as applicable), 4 and 5 masses
- Device Adverse Events/Effects
- Reason for End of Study

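### Low priority: exclusion 3 ties photo-toxicity to an agent taken now or within 72 hours, so some subjects with active photo-toxicity pass it

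*Combined protocol and SAP*

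**What the plan says.** Section 3.1, exclusion 3, excludes a subject who "Is experiencing photo-toxicity associated with currently taking, or having taken, photosensitizing agents within the previous 72 hours", and gives some sulfur-containing drugs, ampicillin and tetracycline as examples. The synopsis is nearly the same: "Photo-toxicity associated with currently taking, or having taken, photosensitizing agents within the previous 72 hours". It leaves out the opening two words and the drug examples, but the link between photo-toxicity and the 72-hour agent window is unchanged.

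The neighbouring criteria in 3.1 are:

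- Criterion 2 excludes skin conditions and breast impediments, with rash among its examples, "which could interfere with the intended field of view".
- Criterion 4 covers current phototherapy.
- Criterion 5 covers photosensitive disease or treatment for one, and carries its own qualifier about present photosensitivity.
- Criterion 6 covers a past adverse reaction to a medical laser procedure.

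All criteria are confirmed before each scan. Section 4.3 lists "Inclusion/Exclusion criteria review" among the data to be collected but does not list medication use. Section 8.3 names phototoxicity among the anticipated risks, and 8.4 states that subjects have no direct benefit.

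**The concern.** A 72-hour look-back on a drug usually works as a washout: anyone who took it recently waits. Here the look-back only describes the cause of a reaction that must already be present. That leaves two groups outside criterion 3:

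1. Subjects with active photo-toxicity whose agent was stopped more than 72 hours earlier.
2. Symptom-free subjects who took such an agent recently, even on the day of the scan.

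What is at stake is avoidable laser exposure of skin that is reacting, or may be prone to react, to light. The plan itself lists that effect as a risk, and the study offers subjects no direct benefit. The stake is subject safety and a clear eligibility rule; the estimates are not affected.

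**Working it through.** The plan gives no figure to reproduce. The check is of logic, with a short count for scale.

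**Step 1. Cases under criterion 3**, taking any reaction to be on the skin to be scanned.

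| Case | Photo-toxicity now | Agent now or within 72 h | Criterion 3 as written | Reworded on symptoms only | Reworded plus separate washout |
|---|---|---|---|---|---|
| A | yes | yes | excluded | excluded | excluded |
| B | yes | no, stopped earlier | passes | excluded | excluded |
| C | no | yes | passes | passes | excluded |
| D | no | no | passes | passes | passes |

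**Step 2. Compare with each possible intent.** A symptom-based rule should exclude A and B. The text excludes only A, so the one thing the 72-hour limit does is release B. A washout should exclude A and C. The text again excludes only A, so the symptom condition releases C. Neither intent is met.

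**Step 3. Look for a backstop.** Criterion 2 may catch a visible reaction in case B, but its test is whether the image could be disturbed, not whether the skin is safe to illuminate. Criteria 4, 5 and 6 concern phototherapy, photosensitive disease and past laser reactions. None addresses a drug reaction in someone without those histories. Concomitant medication is mentioned only as an attachment to the SAE/USADE form (10.1.5).

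**Step 4. Who may receive the laser.** From sections 3 and 5 (footnote 2 to Table 1), BI-RADS 3 to 5 masses are scanned with both probes: 8 + 8 + 4 + 4 + 6 = 30 subjects. BI-RADS 1 and 2 may also be scanned with the duplex probe: 4 + 4 = 8. So 30 to 38 subjects are concerned in all. How many take photosensitizing drugs is not given.

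**Step 5. Earlier safety data, all Gen 1.**

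- PIONEER (1.3.3): 10/1,972 = 0.51% of subjects had OA-related adverse events. The events were 7 paraesthesia and one each of second-degree burn, procedural pain, erythema and warm skin: 7 + 1 + 1 + 1 + 1 = 11. All were mild and none was termed phototoxicity. For 0/1,972 the exact two-sided 95% upper limit is 1 - 0.025^(1/1972) = 0.19%.
- Reader-02 (1.3.4): 3/480 = 0.6% had procedure-related adverse events, all mild.

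These are rates in whole study populations. They do not give the risk in cases B or C.

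**The case against.** The strongest reply is that a symptom-based rule is deliberate. Criterion 5 has a similar qualifier, and two symptom-tied criteria in one list look more like a policy than a slip. This stands as regards case C: admitting symptom-free users may be a considered choice, and the documents do not show it to be wrong. It does not rescue case B, because a symptom-based policy has no use for a time limit on the agent.

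The second reply is that case B is nearly empty. Criterion 2 names rash, needs only possible interference, and in the synopsis refers to skin where the duplex probe will touch. Many visible reactions would be caught. This makes the gap smaller, but leaves subject protection resting on an image-quality test.

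Third, physical exposure is limited. Section 8.1 gives fluence below 20 mJ/cm^2 at any point, and 8.5 places exposure below known skin limits. This supports low priority. The documents do not say whether those limits hold for drug-sensitized skin, nor whether the named drugs sensitize skin at the two laser wavelengths.

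A reader might infer more than the text supports in two ways:

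- That a Gen 1 safeguard was relaxed, since the feasibility study excluded "subjects on medications that could activate dermatologic conditions (e.g. photosensitive skin conditions" (1.3.1). That is a one-clause summary, not the criterion itself, and the summaries of the later studies do not report their exclusions on this point.
- That nothing at all stops a recent user from being scanned. Section 4.4 refers to a separate Scan Protocol that is not part of these documents, so whether it contains a drug check cannot be seen.

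**Conclusion.** The wording defect is real and its priority is low. As written, criterion 3 fails to exclude active photo-toxicity from an agent stopped more than 72 hours earlier, and criterion 2 covers that only in part. It also admits symptom-free recent users, which may or may not be intended.

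This rests on a literal reading of 3.1 and the synopsis, and on the documents supplied. At most 38 subjects are concerned; how many fall into either gap is unknown. Expected harm is small on the stated fluence and the mild Gen 1 adverse events, although those data say nothing specific about drug users. It would go too far to conclude that the study exposes subjects to a demonstrated hazard, or that a medication washout is required: the documents establish neither. No endpoint, analysis or sample-size figure depends on this point.

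**What to change.** Reword exclusion 3 as: *Is experiencing photo-toxicity or drug-related photosensitivity affecting the area to be scanned, whenever the agent was taken.* Use identical text in the synopsis. This closes case B whichever intent was meant.

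If the 72 hours was meant as a washout, add a separate excluding item: *Is taking, or has taken within the previous 72 hours, a photosensitizing agent.* Ask it at the existing pre-scan eligibility check. Whether to add it, and for which drugs, is a clinical decision for the sponsor. If it is not added, the protocol should say that the rule is symptom-based.

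The current text has no body-site limit, whereas the proposed wording has one so as not to exclude for a local reaction that the probe never touches. If the sponsor wants to keep excluding a reaction elsewhere on the body that is tied to a recent drug, it should drop the site phrase or adopt the washout item.

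The cost is a wording change in two places and, with the washout, one more question at a check already made, with possibly a few subjects deferred or not enrolled.
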